**Table 4. Hb-related Safety Endpoints from First Dose Date to Last Visit**

| Variable   | Criterion for "yes"   |
|--|---|
| Hb >12.0 g/dL                                    | Any Hb >12.0 g/dL after Day 1   |
| Hb >13.0 g/dL                                    | Any Hb >13.0 g/dL after Day 1   |
| Hb >14.0 g/dL                                    | Any Hb >14.0 g/dL after Day 1   |
| Hb increase >1.0 g/dL within any 2-week interval | Difference between 2 Hb values within any 2 weeks >1.0 g/dL after Day 1 |
| Hb increase >2.0 g/dL within any 4-week interval | Difference between 2 Hb values within any 4 weeks >2.0 g/dL after Day 1 |
| Hb <9.0 g/dL                                     | Any Hb <9.0 g/dL after Day 1  |
| Hb <8.0 g/dL                                     | Any Hb <8.0 g/dL after Day 1  |

Hb: hemoglobin

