7.2 Inclusion Criteria

Subjects must meet all of the following inclusion criteria to be eligible:

1. At least 18 years of age
2. Diagnosis of CKD with an estimated glomerular filtration rate (eGFR) ≤ 60 mL/min/1.73 m² using the 2009 Chronic Kidney Disease Epidemiology Collaboration (CKD-EPI) creatinine equation during Screening (see [Appendix B: CKD-EPI Creatinine Equation](#)) and not expected to start dialysis within 6 months of Screening

3. Currently maintained on ESA therapy with a dose received within 6 weeks prior to or during Screening
4. Mean Screening Hb between 8.0 and 11.0 g/dL (inclusive) in the US and between 9.0 and 12.0 g/dL (inclusive) outside of the US, as determined by the average of 2 Hb values measured by the central laboratory during Screening
5. Serum ferritin ≥ 100 ng /mL and TSAT $\geq 20\%$ during Screening
6. Folate and vitamin B₁₂ measurements \geq lower limit of normal (LLN) during Screening
7. Understands the procedures and requirements of the study and provides written informed consent and authorization for protected health information disclosure.

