11.7.3 Remaining Safety Endpoints

The analysis of the following safety endpoints will be detailed in the SAP:

The analysis of proportion of subjects with Hb >12.0 g/dL, >13.0 g/dL, or >14.0 g/dL post-Baseline will classify a subject as a “yes” if:

- Any value Hb >12.0 g/dL at any time after Day 1
- Any confirmed value Hb >12.0 g/dL at any time after Day 1
- Any value Hb >13.0 g/dL at any time after Day 1
- Any confirmed value Hb >13.0 g/dL at any time after Day 1
- Any value Hb >14.0 g/dL at any time after Day 1
- Any confirmed value Hb >14.0 g/dL at any time after Day 1.

A Hb value above a set threshold will be considered as confirmed if there are 2 consecutive values above that threshold. The second of the 2 consecutive assessments should be done at

most 12 weeks after the first assessment. Subjects with no available data post-Baseline will be excluded from this analysis. All other subjects will be classified to the “no” category.

The analysis of proportion of subjects with any Hb increase >1.0 g/dL within any 2-week interval or >2.0 g/dL within any 4-week interval post-Baseline will classify a subject as a “yes” if at least 1 of the following criteria at any point after Day 1 is met:

- Hb increase >1.0 g/dL within any 2-week interval
- Hb increase >2.0 g/dL within any 4-week interval.

Subjects with no available data post-Baseline will be excluded from this analysis. All other subjects will be classified to the “no” category.

Observed values of continuous and categorical parameters and changes from Baseline for continuous parameters to each study visit will be summarized descriptively for vital signs and clinical laboratory results. Graphical displays of selected laboratory parameters will also be provided.

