## 1 INTRODUCTION

This statistical analysis plan (SAP) covers the two PRO2TECT studies, Protocols AKB-6548-CI-0014 and AKB-6548-CI-0015, hereafter referred to as CI-0014 and CI-0015, respectively.

The SAP supports the Statistical Methods Section of the clinical study reports (CSRs). It elaborates upon the protocol-specified endpoint definitions and the formal statistical methods that will be used in analyzing both studies. Unless otherwise specified, all analyses will be conducted for each study separately.

Throughout this SAP, planned analyses of both studies are identical to each other except in those places that specifically identify where the plans diverge. Akebia does not intend to pool data together for formal efficacy and general safety analyses; however, analyses of major adverse cardiovascular events (MACE) will be pooled from both studies. A separate SAP will describe the planned methodology for the MACE analyses.

If the analyses described in the protocols differ from those in this SAP, the methods of the SAP prevail.

This SAP contains language and programming code that specifies the exact intent of each analysis. The sponsor will finalize and sign this document prior to locking the database and unblinding (see [Section 2.5](#)). Many of the analyses described in this SAP are quite complex. A blinded team of clinicians and statisticians will review the data carefully to develop conventions and analytic methods not anticipated in writing this SAP.

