## 2.3 Target Hb Ranges

In several places, this SAP refers to the following target Hb ranges as specified in the 2 protocols:

- US target: 10-11 g/dL
- EU, ROW target: 10-12 g/dL

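### The SAP drops the protocol's confirmed-value analyses of Hb >12.0, >13.0 and >14.0 g/dL without explanation; the loss matters most for >12.0 outside the US

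*SAP*

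**What the plan says.** Protocol 11.7.3 (current text, Amendment 7-COL) classifies a subject on the high thresholds in two ways. For each of >12.0, >13.0 and >14.0 g/dL there is an any-value row and a companion row, such as "Any confirmed value Hb >12.0 g/dL at any time after Day 1". A value counts as confirmed when two consecutive values lie above the threshold, the second no more than 12 weeks after the first. The section also says that the SAP will give the details of these analyses.

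SAP Table 4 has one row per threshold, of the form "Any Hb >12.0 g/dL after Day 1". SAP sections 7 and 10.2 and Appendix D.1 likewise contain no confirmed version. On precedence, SAP section 1 states: "If the analyses described in the protocols differ from those in this SAP, the methods of the SAP prevail".

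Three further provisions bear on the size of the issue:

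- **Entry range** (Protocol 7.2): "Mean Screening Hb between 8.0 and 11.0 g/dL (inclusive) in the US and between 9.0 and 12.0 g/dL (inclusive) outside of the US".
- **Dosing target** (SAP 2.3): "US target: 10-11 g/dL" and "EU, ROW target: 10-12 g/dL".
- **Values that count** (SAP 10.2): every central laboratory value in the database. Protocol 9.3.5 schedules 16 of them in Year 1.

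For low Hb, Table 4 has single-value rows such as "Any Hb <9.0 g/dL after Day 1". The protocol never had confirmed rows for low Hb.

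**The concern.** A safety analysis that the protocol specifies has disappeared from the document that governs the analysis, and no reason is recorded.

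The confirmed rows separate a sustained excursion from one value that strays over a line. That distinction matters little for a threshold far from where subjects are meant to be. It matters a good deal for >12.0 g/dL outside the US: a subject may enter with a screening mean of exactly 12.0 and is then treated towards a range whose upper end is 12.0. With 16 scheduled chances in Year 1, a subject managed exactly as intended can become a yes through one ordinary fluctuation.

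Two things are at stake. The reported proportion >12.0 would mix isolated crossings with sustained overshoot. In addition, crossings common to both arms pull the planned odds ratio for a real difference towards 1.

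**Working it through.** **No plan figure to reproduce.** The documents give neither an expected excursion rate nor a within-subject SD. The only Hb SD among the design assumptions is 1.5 g/dL (SAP 2.7), which is the SD of change from baseline. If all of it were visit noise s, with two baseline and four evaluation-period values averaged, then s × √(1/4 + 1/2) = 1.5 and s = 1.73 g/dL. That is only a loose upper bound, so the visit SD below is an assumption.

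**One subject.** Take a stable true level μ, independent normal visit noise s and n = 16 values.

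- Single visit: p = 1 − Φ((12.0 − μ)/s).
- Any value: 1 − (1 − p)^16.
- Confirmed: the probability of at least one run of two in 16. The 12-week limit never binds in Year 1, where visits are 2 or 4 weeks apart.

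| μ (s = 0.5) | p | Any value >12.0 | Confirmed >12.0 |
|---|---|---|---|
| 11.0 | 0.0228 | 31% | 0.8% |
| 11.5 | 0.159 | 94% | 29% |
| 12.0 | 0.5 | about 100% | 96% |

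The last row does not depend on s. Confirmation removes nearly all noise counts in mid-target and very few at the limit.

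**Non-US population.** Assumptions: true Hb with mean 10.4-10.7 and SD 0.7; entry on the mean of two screening values within 9.0-12.0; s = 0.4-0.6; no drug effect; values rounded to 0.1. Results of a Monte Carlo run with 300,000 simulated subjects per scenario:

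| Mean | s | Any value | Confirmed | True level >12.0 |
|---|---|---|---|---|
| 10.4 | 0.4 | 8.7% | 2.0% | 0.3% |
| 10.4 | 0.6 | 21.1% | 4.3% | 0.4% |
| 10.7 | 0.4 | 15.7% | 4.3% | 0.8% |
| 10.7 | 0.6 | 32.3% | 8.4% | 1.0% |

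This gives 9-32% against 2-8%. With a correlation of 0.5 between successive visits, the last row becomes 28.5% and 13.0%.

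**Second model.** Spread true levels evenly over the non-US target of 10-12, so that nobody is truly above 12.0. For s = 0.3, 0.5 and 0.8, the any-value rates are 27%, 44% and 69%, and the confirmed rates 12%, 19% and 31%.

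**Dilution.** Shift everyone by +0.2 g/dL in the first model. The any-value risk ratio for >12.0 runs from 42.6/32.3 = 1.3 to 14.5/8.7 = 1.7. The confirmed ratio runs from 14.2/8.4 = 1.7 to 4.4/2.0 = 2.2.

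**The 12-week limit after Week 52.** Visits are mostly 12 weeks (84 days) apart, with windows of ±10 days (Protocol section 9). Take each visit day as uniform over its 21 days. The two deviations are equal with probability 1/21, so P(gap > 84 days) = (1 − 1/21)/2 = 10/21 = 48%. The 16-week intervals (Weeks 88-104, 140-156 and 192-208) span 112 ± 20 days, at least 92, so no scheduled pair there can ever confirm.

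**The case against.** The strongest reply is that the any-value rows are the protocol's own. A reader might infer that the SAP introduced single-value counting; it did not. It removed the companion rows, and the noise in the remaining rows is the same either way. The protocol also leaves the detail to the SAP, and its endpoint list in 5.4 names no confirmed version. All of this stands. It leaves an unexplained omission of an analysis that Protocol 11.7.3 spells out.

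A reader might also extend the noise argument to <9.0 and <8.0 g/dL because those values equal entry floors. The documents do not support that. Nothing was dropped there, and both arms are dosed towards 10 g/dL or above. With true means at mid-target, the same kind of simulation gives any-value rates of about 3-11% for <9.0 outside the US and 0.3-2% for <8.0 in the US.

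Nor do the documents support calling the proportions uninterpretable, or biased towards one arm. Both arms follow the same visit schedule (SAP 2.5), so noise raises both. Most safety analyses are descriptive (SAP section 10). Table 4 also has >13.0, >14.0 and rate-of-rise rows that sit on no entry limit, and the in-target endpoints of SAP 6.3.2 partly cover sustained departures in Weeks 24-52.

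Finally, confirmed rows are the less sensitive test: for a shift of +0.2 to +0.3 g/dL the z statistic is about 20% lower. That is a reason to keep the any-value rows, not a reason to omit the others.

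**Conclusion.** The point holds as an unexplained loss of a protocol-specified analysis at three high thresholds. It has practical weight mainly for >12.0 g/dL outside the US. There, most stable subjects counted on a single value would be isolated crossings: 9-32% on any value, 2-8% confirmed, and at most about 1% truly above.

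Those figures rest on assumptions that the documents neither give nor contradict: a within-subject SD of 0.4-0.6 g/dL, a stable true level and independent noise. Correlated noise narrows the gap (29% against 13% in the upper case) but does not close it. In the US, where the target stops at 11 g/dL, the issue is small unless the SD is large: with levels spread over 10-11, any-value rates for >12.0 are 0%, 6% and 42% at s = 0.3, 0.5 and 0.8.

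Confirmation is also not a full cure. A subject whose true level is 12.0 is still confirmed 96% of the time, so the display by region and baseline Hb is part of the remedy. This is a cheap improvement to safety reporting. It does not touch the primary efficacy or MACE conclusions.

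**What to change.** In SAP 10.2, Table 4 and Appendix D.1:

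1. Restore the confirmed rows for >12.0, >13.0 and >14.0 g/dL beside the any-value rows. If the sponsor prefers to leave them out, state why.
2. Define confirmation as the next available central value, scheduled or unscheduled, also above the threshold, within a limit that covers the scheduled interval plus its windows. After Week 52 that means 84 + 20 = 104 days for 12-week intervals and 112 + 20 = 132 days for 16-week intervals. The protocol's 12-week limit should not be carried over unchanged.
3. Show >12.0 separately for US and non-US subjects and by baseline Hb, with a category close to 12.0 (for instance 11.5 and above). The planned estimates are stratified by the randomization factors. However, SAP section 11 limits subgroup displays to the primary and secondary efficacy endpoints, and the entry-Hb split at 10.0 does not isolate subjects near the ceiling.
4. Confirmed rows for <9.0 and <8.0 g/dL may be added. They would be new, not a restoration.

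The cost is a few lines of SAP text and some table rows from data already collected. The confirmed rows have fewer events and less power, which is why the any-value rows remain.

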## 10.3 Adverse Events and Serious Adverse Events

The AE CRF has been designed to capture all events after randomization. A TEAE is one that begins or worsens after treatment initiation. The AE reporting period for this study begins upon randomization and ends at the final protocol-required study contact. In addition, any AE that occurs after the AE reporting period is to be reported as an AE if the Investigator assesses it as possibly or probably related to the study medication.

Serious adverse events (SAEs) will be handled in a fashion analogous to the methods described for AEs.

Each AE will be summarized by Medical Dictionary for Regulatory Activities (MedDRA) system organ class (SOC) and preferred term (PT). All AE summaries will provide the number of subjects reporting at least 1 AE. Tables will present the number and percentage of subjects by treatment group reporting at least 1 of the following:

- Treatment-emergent AE (TEAE), SOC, and PT
  - TEAE leading to withdrawal of study medication, SOC, and PT
  - TEAE, severity, SOC and PT
  - Drug-related TEAE, SOC, and PT
  - Drug-related TEAE leading to withdrawal of study medication, SOC, and PT

Statistical Analysis Plan AKB-6548-CI-0014 and AKB-6548-CI-0015

- Treatment-emergent SAE, SOC, and PT
  - Drug-related treatment-emergent SAE, SOC, and PT
  - Fatal TEAE, SOC and PT

A summary table will show number of subjects with at least 1 of each of the following:

- TEAE
- Severe TEAE
- TEAE leading to withdrawal of study medication
- Drug-related TEAE leading to withdrawal of study medication
- Drug-related TEAE
- Treatment-emergent SAE
- Drug-related treatment-emergent SAE
- Fatal TEAE

A summary by treatment group and PT will be presented of TEAEs reported by at least 5% of subjects in either treatment group.

AE summaries will be ordered by decreasing pooled percentage for SOC, and PT within SOC.

TEAEs will be summarized by 1) worst severity, and 2) worst causality by SOC and PT. For each subject and each PT, the worst severity recorded will be used in the by-severity summaries. Similarly, the worst causality (most related to treatment) will be attributed and used in the by-causality summaries. If severity or causality is missing, data will be imputed to the worst category.

A by-subject listing of all TEAEs will be provided. This listing will be presented by treatment group and will include: center, subject identifier, age, sex, race, AE (SOC, PT, and verbatim term), study day of onset, study day of resolution, duration, severity, seriousness, relationship to the study medication, action taken, outcome and causality.

AESI, listed in [Appendix F](#), will be summarized by treatment group. The number and percentage of subjects reporting these AESI will be provided.

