7.5.5.2 Permanent Discontinuation of Study Medication

Subjects who permanently discontinue study medication prior to global study completion are expected to continue to be followed post discontinuation of study medication. These subjects are to have their EOT visit at the time of permanent discontinuation of study medication have the Follow-up visit 4 weeks after the EOT visit and continue to be followed through global study completion. At global study completion, each subject will have an End of Study (EOS) assessment to complete participation in the study. Receipt of rescue therapy is not a reason for permanent study medication discontinuation. While receiving ESA rescue, subjects must temporarily discontinue study medication but should resume study medication following the end of rescue therapy.

For subjects who permanently discontinue study medication, the Investigator will resume standard of care treatment, including ESAs and iron therapy, as deemed appropriate.

It is important to continue to follow subjects that permanently discontinue study medication.

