10.3.1 Reporting Period

The AE reporting period for this study begins from time of randomization through global study completion.

In addition, any AE that occurs subsequent to the AE reporting period that the Investigator assesses as related to the study medication should also be reported as an AE.

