11.7.2 Analysis of Adverse Events

Adverse events will be summarized using the number and percentage of subjects with AEs for all subjects in the safety population. Summaries will also be provided for subgroups including Region, Age, Gender and Race.

All AEs will be coded using MedDRA. Treatment-emergent and post-treatment AEs will be summarized by System Organ Class and Preferred Term for each treatment group. Adverse events will also be summarized by their maximum severity.

Summaries will also be provided for the following types of AEs:

- SAEs
- Related AEs (including all categories for relationship to study medication other than “Unrelated”, as determined by the Investigator)
- AEs leading to early discontinuation of study medication.

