### *Study CI-0015*

- Conversion and Maintenance Period (Weeks 0-52):
  - Weeks 0 to 23: conversion to study treatment for maintaining Hb
  - Weeks 24 to 36: PEP
  - Weeks 40 to 52: SEP

After Week 52, subjects in both studies will proceed to the following 2 periods:

- **Long-Term Treatment Period (Weeks 53-End of Treatment [EOT]):** continued treatment with study medication to assess long-term safety
- **Follow-up Period (EOT + 4 weeks):** post-treatment visit (either in person or by telephone) to assess safety

The duration of the trial will depend on how long it takes for a total of 631 adjudicated MACE to occur in the 2 studies combined. A separate SAP will describe the planned MACE analyses, including the method planned for pooling data from the 2 PRO2TECT studies.

The safety reporting period for a subject enrolled in this study begins upon randomization and ends at the final protocol-required study contact (visit or telephone), also known as a subject's end of study (EOS). In addition, the Investigator should report any adverse event (AE) that occurs after this period if he or she assesses it as possibly or probably related to the study medication.

According to the schedule of visits in the protocol, no laboratory assessments, physical exams, or other procedures are planned after the subject's permanent discontinuation of study medication, also known as EOT; however, AE and rescue therapy assessments, including monitoring for MACE endpoints, will continue until a subject's EOS.

The analysis time periods for efficacy divide the Correction/Conversion and Maintenance periods, Year 1 collectively, into four windows (see [Table 1](#)).

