## 7 NON-MACE SAFETY ENDPOINTS

While the primary safety endpoints relate to MACE, defined as all-cause mortality, nonfatal myocardial infarction, or nonfatal stroke, this SAP addresses only the non-MACE endpoints. As stated above, a separate SAP will describe the analyses of MACE and the individual components of the MACE endpoint as well as expanded MACE definitions where expanded MACE will include hospitalization for heart failure and thromboembolic events.

The safety reporting period for this study begins upon randomization and ends at the final protocol-required study contact. A treatment-emergent adverse event (TEAE) is one that begins or worsens after treatment initiation. The AE CRF has been designed to capture all events after randomization. AEs that occur during the screening period are not reported on the CRF. The treatment groups will be compared with respect to the following non-MACE safety endpoints:

- Adverse events (AEs) and serious adverse events (SAEs)
- Treatment-emergent adverse events (TEAEs) and treatment-emergent SAEs
- Vital signs and clinical laboratory values (see [Appendix E](#))
- Adverse events of special interest (AESI) (see [Appendix F](#))
- Any value of Hb  $> 12.0$  g/dL;  $> 13.0$  g/dL,  $> 14.0$  g/dL,  $< 9.0$  g/dl or  $< 8.0$  g/dl
- An Hb increase  $> 1.0$  g/dL within any 2-week interval or  $> 2.0$  g/dL within any 4-week interval.

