#### **3.2.2 Time to MACE Within 4 Weeks of End of Treatment**

Only a MACE that occurs up to and within 28 days inclusive after permanent discontinuation of study treatment (End of Treatment, EOT) will be included as a MACE Within 4 weeks of End of Treatment.

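### The SAP gives a treatment-emergent AE no end date and drops the protocol's post-treatment AE summary, so the AE tables offer no on-drug comparison

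*SAP*

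**What the plan says.** - **Definition.** SAP 10.3: "A TEAE is one that begins or worsens after treatment initiation". SAP 7 uses the same wording. Only the start is fixed.
- **Collection period.** SAP 10.3: "The AE reporting period for this study begins upon randomization and ends at the final protocol-required study contact". Protocol 10.3.1: "The AE reporting period for this study begins from time of randomization through global study completion". SAP 2.2 adds that, after permanent discontinuation, "AE and rescue therapy assessments, including monitoring for MACE endpoints, will continue until" the subject's end of study. Protocol 7.5.5.4 warns that follow-up may last several years, even after study drug is stopped.
- **Care after stopping.** Protocol 7.5.5.2: "the Investigator will resume standard of care treatment, including ESAs and iron therapy", as judged appropriate. This applies to both arms.
- **Tables planned.** The AE tables in SAP 10.3 are TEAE tables giving the number and percentage of subjects with at least one event. None is limited to time on drug, none covers the post-treatment period, and none is adjusted for exposure.
- **Protocol summaries.** Protocol 11.7.2: "Treatment-emergent and post-treatment AEs will be summarized by System Organ Class and Preferred Term for each treatment group". It defines neither term. SAP 1 states that the SAP's methods take precedence where the two documents differ.
- **MACE.** MACE SAP 3.2.2 has a supplementary analysis limited to events up to and "within 28 days inclusive after permanent discontinuation of study treatment". Protocol 11.7.1 likewise plans a repeat MACE analysis with censoring 4 weeks after discontinuation.

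**The concern.** With no closing date, the label treatment-emergent separates out little more than events between randomization and first dose. A fatal event long after the last vadadustat tablet, in a subject now on a standard-care ESA, is a fatal TEAE in the vadadustat column. The comparator is itself an ESA, so time off vadadustat may be spent on a drug of the comparator class. If an AE is caused by current exposure, adding unexposed time to both arms moves the ratio towards 1. The objective includes safety (Protocol 5.1), so this is the unhelpful direction. The protocol's distinction between treatment-emergent and post-treatment events would have let a reader see it, but the SAP does not carry that distinction through.

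**Working it through.** No sample size, power or decision rule in the documents depends on the TEAE definition, so there is no plan figure to reproduce. What follows is an illustration.

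**From the documents.** Expected mean follow-up is about 2 years (MACE SAP 2.5.1). The 28-day window is taken from MACE SAP 3.2.2.

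**Assumed, because the documents give no values.** Control AE rate λ = 0.05 per year. On-drug hazard ratio HR = 1.5, falling to 1.0 from 28 days after the last dose. A fraction f off drug by 2 years, the same in both arms, with exponential time to discontinuation D. All late AEs are captured.

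**Formulas.** The discontinuation rate is d = −ln(1 − f)/2, which gives 0.112, 0.255 and 0.458 per year for f = 20%, 40% and 60%. The window ends at W = min(D + 28/365.25, 2) years. The risk of at least one AE, averaged over D, is:

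- on-treatment window: E[1 − exp(−λ·HR·W)]
- SAP window: E[1 − exp(−λ·HR·W − λ·(2 − W))]

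In the control arm HR = 1, so the SAP-window risk is 1 − exp(−0.05 × 2) = 9.5% whatever the value of f.

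| Off drug by 2 years | Share of follow-up off drug | On-treatment: vadadustat vs control | Ratio | Difference | SAP window: vadadustat vs control | Ratio | Difference |
|---|---|---|---|---|---|---|---|
| 20% | 10% | 12.6% vs 8.6% | 1.47 | 4.0 points | 13.5% vs 9.5% | 1.42 | 4.0 points |
| 40% | 22% | 11.2% vs 7.6% | 1.47 | 3.6 points | 13.0% vs 9.5% | 1.37 | 3.5 points |
| 60% | 35% | 9.5% vs 6.5% | 1.47 | 3.0 points | 12.5% vs 9.5% | 1.32 | 3.0 points |

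**Wider grid.** With control rates of 0.02 to 0.10 per year and the same values of f, the ratio falls in every case. For HR 1.5 the range moves from 1.43–1.49 to 1.29–1.44. For HR 2.0 it moves from 1.83–1.97 to 1.56–1.87. The risk difference changes by at most about 0.3 points.

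**Does a 28-day window alone cure it?** Let discontinuation differ: 40% off drug by 2 years on vadadustat and 20% on control, with λ = 0.05.

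| True on-drug HR | On-treatment percentages | Ratio | SAP-window percentages | Ratio |
|---|---|---|---|---|
| 1.0 | 7.6% vs 8.6% | 0.89 | 9.5% vs 9.5% | 1.00 |
| 1.5 | 11.2% vs 8.6% | 1.30 | 13.0% vs 9.5% | 1.37 |

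Crude on-treatment percentages would show false protection when there is no effect, and would dilute a real effect more than the SAP's window does. A rate per person-year at risk does not have this fault. With a constant hazard h, expected first events divided by expected time at risk is E[1 − exp(−hW)] / E[(1 − exp(−hW))/h] = h. The rate ratio is then 0.050/0.050 = 1.00 in the first row and 0.075/0.050 = 1.50 in the second.

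**The case against.** The best defence of the SAP is that an open window follows the randomized groups to the end, as the primary MACE outcome does. It also does not suffer from unequal discontinuation, as the last table shows. For events with long latency, such as the malignancies in SAP Appendix F.3, it may be the more sensitive choice. General safety analyses are mainly descriptive (SAP 10), and the formal safety test is on pooled MACE. Some separation is already planned: tables of drug-related TEAEs, tables of TEAEs leading to withdrawal of study medication, and a listing with study day of onset. All of this stands. It is the reason to keep the whole-study tables, but it does not supply an on-drug comparison or restore the protocol's post-treatment summary.

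The volume of late AEs is also uncertain. Protocol 7.5.5.4 makes assessments after discontinuation flexible and requires only end-of-study status. Appendix A footnote [w] says that the reporting period runs to global study completion, but also that AEs are recorded through the follow-up visit, which for a subject who stops early is 4 weeks after the end-of-treatment visit. Thin late capture would mean less dilution, but also an open window observed unevenly.

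A reader might infer three stronger things that the documents do not support:

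- **That the post-treatment summary becomes empty.** The protocol does not define post-treatment AEs or say that they exclude TEAEs. If the term means onset after the last dose, they are a subset of the TEAEs. The summary has been dropped, not emptied.
- **That a subject is off treatment for MACE but on treatment for AEs.** The 28-day MACE outcome is a variation. The primary MACE outcome runs from first dose to end of study (MACE SAP 3.2), as the AE tables do.
- **That the definition hides harm.** Risk differences hardly move, the AE effect and off-drug share are assumed, and the documents do not say how many subjects will resume an ESA.

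**Conclusion.** The concern holds in a limited form. The TEAE definition has no end, so late off-drug events enter the treatment-emergent tables, and a summary named in the protocol is missing from the SAP that overrides it. Under the stated assumptions, a risk ratio of about 1.47 would be reported as 1.42, 1.37 or 1.32, with risk differences unchanged to within about 0.1 point in those three cases. This requires that the drug effect ends soon after stopping and that late AEs are captured. If either fails, the dilution is smaller, and for delayed effects the open window may be preferable. No primary analysis, power statement or decision rule is affected. The gap is in the interpretation of general safety, and it can be closed cheaply.

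**What to change.** In SAP 10.3:

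1. Keep the whole-study AE tables, labelled as covering all follow-up from first dose.
2. Add on-treatment TEAE tables for onset or worsening from first dose to last dose plus 28 days, matching the existing on-treatment MACE analysis. Report exposure-adjusted incidence rates as well as percentages, because crude on-treatment percentages mislead when discontinuation differs by arm.
3. Restore the post-treatment AE table from Protocol 11.7.2, defined as onset after that window.

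Separately, reconcile Schedule of Activities footnote [w] with Protocol 10.3.1, so that the period over which AEs are recorded after early discontinuation is clear.

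The cost is a second set of AE tables, programmed from onset and dosing dates already collected.
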